12.3 Retention of Data

Trial documents (including correspondence related to this clinical study, subject records, source documents, CRFs, study drug inventory records and IRB and sponsor correspondence pertaining to the study, original subject, laboratory, and study drug inventory records relating to the study) will be retained as specified in FDA regulations and institutional policy.

Appendix 1: Diary Card

Medication Diary

Today's date _____

Page 1

Subject's Initials _____ Subject Study ID _____

INSTRUCTIONS TO THE PATIENT:

1. Complete one form for each cycle.
2. You will take your dose PIO each day at approximately the same time. PIO tablets should be swallowed whole, and should not be broken, chewed or opened. You will take ____ mg tablets each day.
3. Record the date, the number of PIO tablets of each size you took, and when you took them.
4. Record the number of TKI tablets of each size you took.
5. **Please bring your pill bottle and this form to your physician when you go for your next appointment.**

Date	Day	Time of daily dose	PIO			TKI _____ _____ mg	Comments
			15 mg	30 mg	45 mg		
	1						
	2						
	3						
	4						
	5						
	6						
	7						
	8						
	9						
	10						
	11						
	12						
	13						
	14						

Subject's Initials _____ Subject Study ID _____

		INSTRUCTIONS TO THE PATIENT:					
		
 1. Complete one form for each cycle. 2. You will take your dose PIO each day at approximately the same time. PIO tablets should be swallowed whole, and should not be broken, chewed or opened. You will take ____ mg tablets each day. 3. Record the date, the number of PIO tablets of each size you took, and when you took them. 4. Record the number of TKI tablets of each size you took. 5. If you have any comments or notice any side effects, please record them in the Comments column. 5. Please bring your pill bottle and this form to your physician when you go for your next appointment. 					

Date	Day	Time of daily dose	PIO			TKI _____ _____ mg	Comments
			15 mg	30 mg	45 mg		
	15						
	16						
	17						
	18						
	19						
	20						
	21						
	22						
	23						
	24						
	25						
	26						
	27						
	28						

	Patient's Signature: _____	Date: _____
--	----------------------------	-------------

	Physician's Office will complete this section:	
	1. Patient's planned daily dose _____ Total number of pills taken this month _____	
	Physician/Nurse/Data Manager's Signature _____ Date : _____	

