3.2 Endpoints

- *Safety*: To describe AEs in subjects receiving the combination of PIO and TKI. AEs will be graded according to the Common Terminology Criteria for Adverse Events (**CTCAE**) v.4.03 assessed through scheduled assessment and subject reported diary
- *Efficacy*: To determine the proportion of subjects who maintain MMR following a second discontinuation of TKI.

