³*CML History, Prior Therapy, and Response:* The initial presentation history and pathology including the date of onset of CML must be recorded. TKI therapy including date of initiation and stop, doses, dose reductions or interruptions will be recorded. Sequential monitoring response to therapy and date of first TKI discontinuation, as well as post-discontinuation monitoring data will be collected. If TKI was restarted prior to enrollment on study, date of re-initiation, and dosing information, as well as response monitoring data will be collected.

⁴*Vital signs and Physical Examination:* Vital signs including temperature, pulse, and blood pressure, and complete physical examination, including weight, must be performed at screening, day 14 and 28 as part of study. After that, this will be done every two to three months as part of standard of care unless new symptoms occur.

⁵*Concomitant medications:* All prescribed, over the counter, and supplemental/herbal medications, including route of administration (oral, topical, intravenous, rectal, subcutaneous, etc.), frequency, and duration will be recorded.

⁶*Complete Blood Count (CBC), differential and Serum Chemistries:* CBC with automated differential and serum chemistries will be obtained at screening as part of standard of care, and day 14 and 28 as part of study. After that, this will be done every two to three months as part of standard of care unless new symptoms occur.

⁷*Urine human chorionic gonadotropin (HCG):* HCG will only be performed in pre-menopausal women of childbearing age with no history of hysterectomy or bilateral tubal ligation.

⁸*Blood qRT-PCR for BCR-ABL1:* Blood qRT-PCR for *BCR-ABL1* will be obtained monthly while on PIO and TKI. Following discontinuation of TKI, monthly blood qRT-PCR for *BCR-ABL1* for the first 3 months, quarterly for a year and bi-annually thereafter will be done as part of standard of care.

⁹*Diary card:* A diary card will be completed daily to indicate the date and approximate time of administration of each dose of PIO and TKI, including any deviations from schedule such as missed or repeated doses. (**Appendix 1**)

¹⁰*Morisky Medication Adherence Scales – 8 (MMAS-8):* A MMAS-8 will be completed at each clinic visits while on PIO and TKI. (**Appendix 2**)

¹¹*Adverse event assessments:* All AEs will be assessed at each clinic visit as part of standard of care regardless the event is considered related to the treatment or not.

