8.3.2 Overdose

An overdose is defined as the accidental or intentional ingestion or infusing of any dose of a product that is considered BOTH excessive AND medically important. All occurrences of overdose must be reported as an SAE. These AEs will be monitored as instructed in the schedule of events and as clinically indicated.

9. Statistical Considerations

9.1 *General Considerations*

For the purposes of this protocol and all analyses, a cycle of treatment is defined as 28 days.

9.2 *Analysis Population*

Intention to treat (ITT) population: The ITT population includes all subjects who are enrolled in the study.

Safety Population: The safety population includes all subjects who have received at least 1 dose of PIO.

Per-protocol Population: The per-protocol population includes all subjects who are enrolled, receive at least one dose of study drug, and have no major protocol violations that could be expected to impact response data, such as: failure to satisfy one or more eligibility criteria, administration of other anti-cancer therapy concurrent with study drug, and administration of incorrect study drug dose. Major protocol violations will be finalized and documented prior to final data analysis.

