9.3 Study Endpoints

The primary endpoint of this study is to determine safety and efficacy of PIO administered in combination with TKI. Therefore, description of AEs in subjects receiving the combination of PIO and TKI will be collected. AEs will be graded according to the CTCAE v.4.03 assessed through scheduled assessment and subject reported diary. Efficacy is determined by the proportion of subjects who achieve and maintain < MR^{4,5} using blood qRT-PCR for *BCR-ABL1* obtained monthly while on PIO and TKI.

Secondary endpoint of the study is to determine the proportion of subjects who lose MMR following discontinuation of PIO and TKI using blood qRT-PCR for *BCR-ABL1* obtained monthly for the first 3 months then quarterly.

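### Only the day 15-28 page of the subject diary asks for side effects, so self-reported adverse events may be recorded unevenly within each cycle

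*Combined protocol and SAP*

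**What the plan says.** The synopsis and sections 3.2 and 9.3 give the safety endpoint two data sources. Section 3.2 has AEs "assessed through scheduled assessment and subject reported diary". Section 9.3, which makes safety part of the primary endpoint, repeats this: "AEs will be graded according to the CTCAE v.4.03 assessed through scheduled assessment and subject reported diary".

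The diary itself (Appendix 1) is a two-page form with the instruction "Complete one form for each cycle", and section 9.1 states that "a cycle of treatment is defined as 28 days". The two pages carry the same table, including a Comments column, but their instructions differ:

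- Days 15-28: "If you have any comments or notice any side effects, please record them in the Comments column". This is the first of two items numbered 5 on that page.
- Days 1-14: items run from 1 to 5 and none mentions side effects. Item 5 is only "Please bring your pill bottle and this form to your physician when you go for your next appointment".

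Footnote 9 to Table 3 (section 5.1) describes the diary's purpose as dosing: "A diary card will be completed daily to indicate the date and approximate time of administration of each dose of PIO and TKI", together with missed or repeated doses. Sections 5.2.3, 5.2.4 and 5.2.7 have staff review the diary card as part of checking compliance. The office section at the foot of the form asks for planned dose and pills taken.

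Separately, footnote 11 provides that "All AEs will be assessed at each clinic visit as part of standard of care". On-treatment visits fall on day 14 ± 2, day 28 ± 2, and every 28 ± 2 days after that.

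**The concern.** The protocol counts the diary as a source for a primary endpoint, but one line on one page is the only operational text that makes it an AE instrument. A subject following the instructions page by page is asked about side effects for the second half of a cycle and not for the first. Because each cycle uses a new copy of the same form, the difference recurs throughout treatment.

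What is at stake is the completeness and dating of self-reported events, chiefly mild or transient ones that a subject may not remember weeks later. Section 6 asks for the timing of AEs, and section 9.5 reports their incidence by grade. The period after the planned dose increase deserves attention because section 1.5.3 describes fluid retention and edema on pioglitazone as dose-related. After day 28, examinations and laboratory tests become less frequent unless new symptoms arise (section 5.2.4), so symptom reports also help decide when those checks are done.

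**Working it through.** There is no figure in the plan to reproduce. The check compares the pages and places them on the study calendar.

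**Inputs.** Cycle length is 28 days (section 9.1). The first diary page covers cycle days 1-14 (Appendix 1). Visits are on day 14 ± 2, day 28 ± 2, then every 28 ± 2 days (sections 5.2.3 and 5.2.4). The dose increase is on day 56 (section 5.2.4).

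**Step 1: share of diary days without the instruction.** 14 / 28 = 50% in every cycle. This counts diary days; it does not measure how many events are captured.

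**Step 2: where the dose increase falls.** For study day d, cycle = floor((d − 1)/28) + 1 and cycle day = ((d − 1) mod 28) + 1.

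- d = 56: cycle 2, day 28.
- d = 57: cycle 3, day 1.
- d = 70: cycle 3, day 14.
- d = 84: cycle 3, day 28.

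Study days 57-70, the two weeks that follow the increase, are therefore on the page without the instruction.

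**Step 3: time to the next scheduled AE assessment** (visit day minus event day).

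| Window on the first page | Next visit | Delay, nominal visit day | Delay, with ± 2 days |
|---|---|---|---|
| Cycle 1, days 1-14 | day 14 ± 2 | 14 − 14 = 0 to 14 − 1 = 13 | up to 16 − 1 = 15 |
| Cycle 2, days 29-42 | day 56 ± 2 | 56 − 42 = 14 to 56 − 29 = 27 | 54 − 42 = 12 to 58 − 29 = 29 |
| Cycle 3, days 57-70 | day 84 ± 2 | 84 − 70 = 14 to 84 − 57 = 27 | 82 − 70 = 12 to 86 − 57 = 29 |

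In cycle 1, a visit held on day 12 leaves days 13 and 14 to the day 28 ± 2 visit, a delay of 26 − 14 = 12 to 30 − 13 = 17 days. Otherwise the day-14 visit closes that window.

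The second page of cycle 3 (days 71-84) has a nominal delay of 84 − 84 = 0 to 84 − 71 = 13 days. From cycle 2 onward the instruction is thus missing from the half of the cycle that lies further from the next visit.

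**Step 4: scale.** If all 26 planned subjects enter the safety population, one subject whose event goes unrecorded changes an incidence by 1 / 26 = 3.8 percentage points. This only shows the scale. The documents give no basis for estimating how many events, if any, would be missed.

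**The case against.** The strongest reply is that the diary only supplements other sources. Scheduled assessment is named first in the endpoint. AEs are assessed at each visit and recorded continuously (sections 5.1 and 5.2.4), volunteered events are reported (section 8.1.3), and unscheduled visits are allowed (section 5.2.6). The form is a single document per cycle, its side-effect instruction carries no date limit, and the first page has a Comments column, so a subject can write down a side effect on any of the 28 days. Non-hematologic dose actions in Table 4 start at grade 2. Where CTCAE gives no definition, section 8.1.5 describes grade 2 as interfering with routine activity, and such an event is less likely to go unmentioned. The AE analysis is descriptive.

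All of this stands, and it limits the point. A reader might infer that the safety endpoint depends on the diary, or that events in days 1-14 are certain to be under-counted. The documents support neither: there is a second source, and no amount of under-capture can be derived. A reader might also infer that the first weeks on pioglitazone go unmonitored. They do not, because the day 14 ± 2 visit includes both AE assessment and diary review.

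The reply does not explain why a named AE source should ask its question on one page and not the other. Nor does it supply a scheduled contact close to days 57-70.

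**Conclusion.** The inconsistency is real and of minor severity. The diary is one of two named AE sources, and half of its days carry no side-effect instruction. Uneven self-reporting between the halves of a cycle is a plausible risk, not a demonstrated bias. It matters most from cycle 2 onward, and notably on study days 57-70, where recall at the next scheduled visit would be about 12 to 29 days. Sample size, power and type I error are untouched.

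The conclusion assumes three things: that the form issued to subjects matches Appendix 1 as published, that visits keep to their stated windows, and that the subject has no unscheduled contact in between. The first should be checked against the form in use. If the line is already on its first page, only the alignment of footnote 9 and the visit review remains.

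**What to change.** 1. Repeat the existing side-effect instruction on the day 1-14 page of Appendix 1.
2. Renumber the day 15-28 page so that only one item is numbered 5.
3. Extend footnote 9 in section 5.1 to say that the diary also records side effects with their dates.
4. In sections 5.2.3, 5.2.4 and 5.2.7, state that staff review these entries as AEs, grading and recording them, as well as using the card for compliance.

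The cost is one repeated sentence on a form and a few words in the protocol, made as a minor amendment. It adds no visits or tests and changes no dose or clinical rule. Staff already review the diary and record AEs at these visits, so the extra work is small.

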Appendix 2: Morisky Medication Adherence Scales – 8 (MMAS-8)

1) Do you sometimes forget to take your pills?	YES=0  NO=1 
2) People sometimes miss taking their medications for reasons other than forgetting. Thinking over the past two weeks, were there any days when you did not take your medicine?	YES=0  NO=1 
3) Have you ever cut back or stopped taking your medicine without telling your doctor because you felt worse when you took it?	YES=0  NO=1 
4) When you travel or leave home, do you sometimes forget to bring along your medicine?	YES=0  NO=1 
5) Did you take all your medicine yesterday?	YES=1  NO=0 
6) When you feel like your symptoms are under control, do you sometimes stop taking your medicine?	YES=0  NO=1 
7) Taking medicine every day is a real inconvenience for some people. Do you ever feel hassled about sticking to your treatment plan?	YES=0  NO=1 
8) How often do you have difficulty remembering to take all your medicine? ___ A. Never/rarely ___ B. Once in a while ___ C. Sometimes ___ D. Usually ___ E. All the time	A=4  B=3  C=2  D=1  E=0  Divide score by 4

Adherence	MMAS-8 Score
High Adherence	8
Medium Adherence	6-8
Low Adherence	<6
